8.3 Recruitment..... 20

8.4 Written Informed Consent 21

8.5 Process of Consent..... 21

8.6 Certificate of Confidentiality..... 22

9. REFERENCES..... 22

10. APPENDICES AND RDCRN INFORMED CONSENT TEMPLATES 23

10.1 Appendix 23

10.2 Informed Consent for Healthy Volunteers 25

10.3 Informed Consent for Urea Cycle Disorder Participants 40

1. Protocol Synopsis

Interventional Synopsis

Protocol Number:	5115
Protocol Title:	Manipulating the Gut Microbiome in Urea Cycle Disorders
Study Chair:	[name] [name]
Study Co-Chair:	[name]
Statistician:	[name]
Consortium:	Urea Cycle Disorders Consortium
Participating Sites:	Children's National Medical Center
Activation Date:	Pending
Current Status:	Pre-enrollment
Sample Size:	Group 1: 8 healthy adult subjects Group 2: 8 adult subjects with urea cycle disorders
Target Enrollment Period:	Group 1: 1 year Group 2: 2 years
Study Phase	I/II
Study Design:	Open-label, cross-over
Primary Study Objective:	The objective is to determine if acetohydroxamic acid (AHA) can prevent hydrolysis of urea by inhibiting the bacterial urease of gut flora of both healthy control adults as well as adults with urea cycle disorders
Secondary Study Objective(s):	Determine if the proposed dose of acetohydroxamic acid is safe

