	
ASA), defined as the presence of argininosuccinic acid in the blood or urine, decreased AL enzyme activity in cultured skin fibroblasts or other appropriate tissue, or identification of a pathogenic mutation in the AL gene
 
A subject may not be included in the study if any one of the following criteria is met:
 
For both Group 1 and Group 2:
 
 - Current or prior Helicobacter pylori infection - Chronic gastrointestinal illness (e.g., inflammatory bowel disease) - Chronic renal failure - Taking probiotic medications within a week of study start date - Currently pregnant or lactating. Documentation of a negative pregnancy test within a week prior to testing is required, unless pre-menarchal or menopausal, experiencing menses that week, or other circumstances which preclude pregnancy (e.g. hysterectomy). - Presence of acute infection at the time of inclusion - Participation in any other clinical interventional trial or received experimental medication within the last 30 days - Any clinical or laboratory abnormality or medical condition that, at the discretion of the investigator, may put the subject at an additional risk by participating in this study
Treatment	
Agent-	Acetohydroxamic Acid (AHA, Lithostat)
Dosage, schedule, route of administration-	Single dose, 60 mg/kg PO
Safety Issues-	Bone marrow depression (leukopenia, anemia, and thrombocytopenia) has occurred in experimental animals receiving large doses of AHA. However, only a single dose will be administered in this study, and is not likely to result in this adverse effect.
Primary Outcome Measures:	Difference in the time-averaged level of blood $^{13}\text{CO}_2$ after a single bolus of intravenous [^{13}C]-Urea, measured on two occasions: once at baseline, and once 2-hr after an oral bolus of AHA
Secondary Outcome Measures:	Differences in blood [^{13}C]-Urea, Urea, Ammonia, Glutamine
Safety Variables	Hemoglobin, White blood count, platelets, AST, ALT, Bilirubin, Creatinine
Statistical Considerations (sample size and analysis plan):	Longitudinal linear regression models will assess and compare time averaged mean changes in blood $^{13}\text{CO}_2$, and blood levels of [^{13}C]-urea, ammonia and glutamine. A sample size of 8 crossover participants provides 90% power to detect a 20% relative difference in the time-averaged level of $^{13}\text{CO}_2$ in treatment with AHA versus non-AHA under a 2-tailed type I error of 0.05.

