1.1 Overview

This project will study the efficacy and safety of the pharmacologic blockade of urease in the nitrogen salvage pathway of intestinal microbes in subjects with partial urea cycle disorders. Additional trapping of ammonia as excretable urea may result in improved nitrogen excretion and reduced ammonia levels.

Urea cycle disorders (UCDs) are a group of disorders resulting from a complete or partial deficiency of one of the 6 enzymes or 2 transporters that comprise the urea cycle, the essential biochemical pathway which converts toxic ammonia into urea. These disorders have as a common feature, a reduced or complete inability to convert ammonia into urea, thereby resulting in high ammonia levels, or hyperammonemia. If untreated, hyperammonemia may result acutely in lethargy and coma, and chronically in intellectual disability. Current treatment for hyperammonemia is suboptimal, thus the search for new treatments is critical.

The urease inhibitor, acetohydroxamic acid (AHA, Lithostat®, Mission Pharmacal), is an FDA-approved product for another indication- the treatment of struvite nephrolithiasis in chronic urinary tract infections in both adults and children^{1,2}.

It is known that many urea-splitting bacteria also exist in the gut, and that in healthy individuals, approximately 15-30% of blood urea is degraded via gut bacteria into ammonia³, which returns to the liver via the portal vein, only to be recycled into urea. This percentage of degraded urea may even be greater in patients with urea cycle disorders, who are on a low protein-diet⁴ and whose gastrointestinal contents thus likely have lower nitrogen content, promoting bacterial recycling of nitrogen from available urea. Additionally, urea hydrolysis has been shown to be greatest in infants⁵, precisely the age at which hyperammonemic episodes are the most frequent in UCD patients.

We intend to study if AHA can inhibit gut bacteria degradation of urea, thereby reducing the quantity of ammonia returning to the liver. We intend to investigate this by studying subjects on two occasions at least 3 days apart:

On the first occasion, subjects will receive an intravenous dose of ¹³C-urea. Following the intravenous bolus of ¹³C-urea, over the subsequent 4 hours, we will collect several sequential measurements of blood and urine biomarkers from an IV catheter placed in the other arm. The intent is to obtain baseline ¹³CO₂ kinetics in the subject.

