On the second occasion, subjects will first receive an oral dose of AHA approximately 1 hour prior to the intravenous ¹³C-urea dose. Similar sequential measurements of blood and urine biomarkers will be performed. The intent is to observe a reduction in ¹³CO₂ when AHA is administered.

We intend to initially study a cohort of unaffected adult subjects. If successful, we will study adults with partial urea cycle disorders.

This study will be conducted in the Clinical Research Center (CRC) of the Clinical and Translational Research Institute (CTSI) of Children's National Medical Center (CNMC).

2. Specific Aims (Hypothesis and Objectives)

The specific aim is to investigate whether a single oral dose of AHA can inhibit intestinal bacterial urease in healthy subjects as well as in patients with partial UCDs, and whether it is safe. We propose a study with two components: the first without AHA, and the second after a single dose of AHA, 60mg/kg/d. We will evaluate whether AHA will inhibit bacterial urease, by measuring ^{13}C -labeled urea in blood and urine samples, following an intravenous load of ^{13}C -urea. Blood and urine ^{13}C -urea, plasma ammonia, plasma glutamine and blood urea will also be measured.

3. Background

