Enteral AHA has previously been administered to patients with hyperammonemia due to hepatic encephalopathy in two published reports^{6,7}. A single dose of oral 750 mg in adult patients was insufficient to result in any change in ammonia after 90 minutes in cirrhotic subjects free of *H. Pylori*⁷. However, in encephalopathy cirrhotic subjects administered AHA 20-60 mg/kg via naso-gastric tube, a statistically significant decreased in blood ammonia was observed⁶, with the effect most striking in subjects receiving a dose of 40-60 mg/kg/d.

This proposal would introduce a novel therapeutic approach for patients with UCD using a low-toxicity compound that may be particularly effective in patients with partial UCDs. There are two potential ways this approach may lower blood ammonia or excess nitrogen. The first is through blockage of new ammonia formation from urease. The second path may be increased consumption of residual dietary nitrogen by the gut flora in the absence of available nitrogen released through urease. Both effects may decrease the amount of nitrogen entering the portal vein. This new therapy will not interfere with other therapies, but would be complementary to them and may potentiate the nitrogen trapping effects of arginine and citrulline by preventing the degradation of the urea produced by their administration.

4. Study Design and Methods

This pilot crossover study will first evaluate the impact of AHA versus non-AHA primarily on ¹³CO₂ and secondarily on other biomarkers in healthy adults before applying the same crossover design to UCD subjects. A randomization table will determine if AHA or non-AHA will be performed first.

The figure below illustrates our study design:

Subjects will be required to fast for a minimum of 4 hours prior to beginning the study. Food consumption will not be permitted during the study; however subjects will be allowed to drink water or pedialyte throughout the study. Subjects will be observed and

various biomarkers will be collected throughout the 4-6 hours that they are studied. 5 mL of blood will be collected at each of the 7 time points shown above. Administration of [¹³C]-urea will be completed through an intravenous catheter. Blood draws will be done through the placement of a Heplock intravenous catheter on the opposite arm from where [¹³C]-urea was first administered. If there is not adequate vascular access, subjects will have a PICC (peripherally inserted central catheter) line placed instead.

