4.6 Schedule of Events

Subjects will be studied twice: once without and once with a single dose of acetohydroxamic acid, with the two study days at least 3-days apart.

Table 1. Laboratory investigations (each study day)

	Time point (min)							
	Baseline	0	30	60	90	120	180	240
Blood [¹³ C]-urea		X	X	X	X	X	X	X
Blood urea		X	X	X	X	X	X	X
Plasma glutamine		X	X	X	X	X	X	X
Ammonia		X	X	X	X	X	X	X
Blood ¹³ CO ₂		X	X	X	X	X	X	X
Urine [¹³ C]-urea		X						X
Urine urea		X						X
Safety labs:								
Hemoglobin	X							X
White blood count	X							X
Platelets	X							X
AST	X							X
ALT	X							X
Bilirubin	X							X
Creatinine	X							X

'Baseline' indicates at a time 0 on days when AHA is not administered or at a time prior to AHA administration on the days where AHA is administered. In addition, some of the blood and urine samples will be saved at the Clinical and Translational Science Institute at CNMC for up to 3 years after the conclusion of the study to test for the metabolism of AHA, after which the samples will be discarded.

5. Safety Monitoring

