10.1 Appendix

Drug Information:

Acetohydroxamic acid (Lithostat)

Pharmacology and Pharmaceutical Information:

Acetohydroxamic acid (AHA) is a stable, synthetic compound derived from hydroxylamine and ethyl acetate. It is a urease inhibitor that reversibly inhibits bacterial enzyme urease, thereby inhibiting the hydrolysis of urea and production of ammonia in urine infected with urea-splitting organisms. AHA is available for oral administration as 250 mg white, round tablets and manufactured by Mission Pharmacal. The intact drug is stored at controlled room temperature (20–25°C)

Treatment Information:

All subjects (healthy adults and UCD patients) will receive a single oral dose of 60 mg/kg acetohydroxamic acid during one of the treatment periods, based on the randomization assignment determining whether treatment occurs in the first or the second treatment cycle; doses will be rounded “up” or “down” to the nearest 250 mg to coincide with the available dosage form since the tablets cannot be scored. Patients will be instructed to fast for 4 hours prior to the study; subsequently, the ¹³C-Urea tracer will be administered 60 minutes after the ingestion of the acetohydroxamic acid dose.

¹³C-Urea

¹³C-Urea is a stable isotope produced by Cambridge Isotope Laboratories, Inc., Tewksbury, MA. The GMP grade pharmaceutical product is provided to Children’s National Medical Center as a sterile bulk powder.

Treatment Information:

All subjects (healthy adults and UCD patients) will receive a single IV infusion of ¹³C-Urea administered over 10-15 minutes, during both treatment cycles. The infusion will be prepared at a dose of 6 mg/kg and infused via a peripheral IV.

Preparation of ¹³C-Urea for Intravenous Use

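### The Overview fixes the visit order (no AHA first, AHA second) while Section 4 and the Appendix randomise it; under the Overview's order, AHA and visit cannot be separated

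*Combined protocol and SAP*

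**What the plan says.** Two accounts of the visit order stand in the current text.

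**Fixed order.** In Section 1.1, "On the first occasion, subjects will receive an intravenous dose of" labelled urea, to establish each person's baseline kinetics. Then "On the second occasion, subjects will first receive an oral dose of AHA approximately 1 hour prior to the intravenous" tracer. This applies to all subjects. Two other places lean the same way, although each can be read without a time order:
- Section 2 (Specific Aims): "We propose a study with two components: the first without AHA, and the second after a single dose of AHA".
- Synopsis, primary outcome: "measured on two occasions: once at baseline, and once 2-hr after an oral bolus of AHA".

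**Randomised order.** Section 4: "A randomization table will determine if AHA or non-AHA will be performed first". Appendix 10.1 places the AHA dose in one of the two periods, "based on the randomization assignment determining whether treatment occurs in the first or the second treatment cycle".

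**No order given.** The Synopsis calls the design "Open-label, cross-over", and Section 4.6 says only "Subjects will be studied twice: once without and once with a single dose of acetohydroxamic acid", with the study days at least 3 days apart.

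Section 6 describes longitudinal linear models with a pretreatment covariate and a random intercept. It names no period term. Neither Section 4 nor the Appendix says that the randomisation table is balanced.

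**The concern.** Under a randomised order some participants may take AHA first; under the Overview none do. Both cannot be followed, and no statement says which governs.

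The difference matters because the primary result is one AHA versus non-AHA contrast in 8 people. Section 6 also requires a clear signal in healthy adults before the UCD group can begin. With a fixed order, anything that differs between first and second visits is counted as an AHA effect. Label left over from the first tracer dose would raise visit-2 ¹³CO₂ and hide a real reduction. A fall at visit 2 from some other cause would look like urease inhibition. With a randomised order, a visit effect gives no bias on average.

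**Working it through.** **1. Can AHA be separated from visit?** Take a within-person model with 8 subject terms, one visit term and one AHA term: 10 columns.
- All participants in the order no AHA, then AHA: rank 9 of 10. The AHA column equals the visit column, so the two effects cannot both be estimated.
- Order randomised 4:4 (or 5:3): rank 10 of 10. Both can be estimated.

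This result does not depend on any assumed effect size or SD.

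**2. Inputs for the illustrations.** From Section 6: n = 8; expected level 0.041% without AHA against 0.033% with it, a difference of 0.008; 20% of 0.041 is 0.0082; precision ±0.0075. Assumptions: 0.0075 is the SD of the within-person difference d (non-AHA minus AHA), since the text says only precision; 0.005 and 0.0106 show the range. Visit effects are hypothetical. The test is a two-sided paired t test at 0.05 with 7 df.

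**3. The plan's own figure.** n = (0.0075 × (1.960 + 1.282) / 0.008)² = 9.2, or 8.8 with 0.0082, against the stated 8. Power at n = 8 for 0.008 is 85.5% by the normal formula and 73.5% by the t test. The stated 90% is not recovered on these inputs. That is a separate matter; 73.5% is the reference value below.

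**4. Fixed order, rise r at visit 2.** The mean of d becomes 0.008 − 0.041r: 0.008, 0.00595 and 0.0039 for r = 0, 5% and 10%. Power from the noncentral t:

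| SD of d | no visit effect | 5% rise | 10% rise |
|---|---|---|---|
| 0.005 | 97% | 82% | 48% |
| 0.0075 | 73.5% | 49% | 25% |
| 0.0106 | 45% | 28% | 15% |

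**5. Fixed order, chance of reaching the 20% signal.** The standard error is 0.0075/√8 = 0.00265. For a true reduction of exactly 20%, P(estimate ≥ 0.0082) = 1 − Φ(0.041r / 0.00265): 50% with no visit effect, 22% with a 5% rise and 6% with a 10% rise.

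**6. Fixed order, fall at visit 2 and no true effect.** The mean of d is 0.041r.
- 10% fall (0.0041): significant in 27% of trials; estimate at or above 0.0082 in 6%.
- 15% fall (0.00615): significant in 52%; at or above 0.0082 in 22%.

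**7. Randomised order.** With a and b participants in the two orders, the share of the visit effect left in an unadjusted estimate is (a − b)/8: 0 at 4:4, 0.25 at 5:3, 0.5 at 6:2. Power for 0.008 with SD 0.0075:
- 4:4 without a period term (200,000 simulated trials): 71% for a 5% visit effect, 62% for 10%, 49% for 15%.
- With a period term (6 df), whatever the visit effect: 71% at 4:4, 68% at 5:3, 59% at 6:2.

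Under simple randomisation with no period term and no true effect, simulated type I error is 4.9–5.3% for 5–15% visit effects.

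**The case against.** Section 4 is the methods section and Appendix 10.1 is the dosing text. Both randomise, and the Overview is an introduction. On that reading the intended design is sound and only a summary is badly worded. This has force: the finding is an inconsistency, not proof that the trial would be confounded. But no order of precedence is stated, and a reader working from the Overview would run a different study.

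The supporting citations differ in strength. The Specific Aims may be listing conditions rather than visits, and Table 1 uses baseline for a time point within each day, so the Synopsis wording need not mean the first visit. The clear conflict is with the Overview. A design figure mentioned in Section 4 is not in the text reviewed and may show the order, but it could not change what the Overview says.

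The magnitudes rest on assumed visit effects and a simple paired test. The planned model uses repeated samples and a pretreatment level, and Table 1 schedules a time-0 ¹³CO₂ sample on each day. If the covariate is specific to each day, it may absorb part of any leftover label, so the losses in step 4 are unadjusted figures for that mechanism. It cannot remove a visit effect that is not already visible at time 0. No particular cause is proposed for a visit-2 fall.

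A fixed order might be defended as avoiding AHA carryover. The documents do not say so. With the 5–10 hour half-life in Section 5.3, 72 hours is at least 7.2 half-lives, leaving under 1% of plasma drug; persistence of any effect on gut flora is not documented.

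The period term brings almost nothing at a 5% visit effect (71% either way at 4:4). It is secondary.

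**Conclusion.** The concern holds. The Overview and the randomisation statements in Section 4 and Appendix 10.1 cannot all be followed. Under the Overview's order the AHA effect is completely confounded with visit, and no analysis term repairs that. This conclusion needs no numerical assumption.

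The practical size is conditional on the Overview being followed and on a visit effect existing. The power and false-positive figures show what modest visit effects could do to the go/no-go contrast; they do not estimate this trial's risk. The 20% signal rule limits false progression more than significance alone does, but it offers no protection against a rise that masks a true effect.

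The missing period term and the unstated balance are lesser points: under randomisation they affect precision, or the estimate in a particular unbalanced split, and cause no bias on average. The wording should be fixed before enrolment.

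**What to change.** Reword Section 1.1 so that it describes one study day with AHA and one without, in the order set by the randomisation table. Bring Section 2 and the Synopsis primary outcome into line, so that neither can be read as fixing the order.

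As secondary improvements:
- State that the table is balanced, with 4 participants per order in each group.
- Add study day (first or second) as a fixed effect in every Section 6 model.

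The cost is wording in three places, one line on how the table is built and one model term. The term uses 1 degree of freedom (7 to 6). With no visit effect, power at 4:4 goes from about 73.5% to 71%; with a 10% or 15% visit effect it stays at 71% instead of falling to 62% or 49%.

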5.8 Data Quality and Monitoring Measures

As much as possible data quality is assessed at the data entry point using intelligent on-line data entry via visual basic designed screen forms. Data element constraints, whether independent range and/or format limitations or 'relative' referential integrity limitations, can be enforced by all methods employed for data input. QA reports assess data quality post-data entry. As we note, data quality begins with the design of the data collection forms and procedures and incorporates reasonable checks to minimize transcription and omission errors. Of the more important quality assurance measures are the internal validity checks for reasonableness and consistency.

- Data Monitoring: The RDCRN DMCC identifies missing or unclear data and generates a data query to the consortium administrator contact.
- Data Delinquency Tracking: The Data Management and Coordinating Center will monitor data delinquency on an ongoing basis.

6. Statistical Considerations

Linear longitudinal regression models will be developed to estimate the change in the time-averaged levels of blood $^{13}\text{CO}_2$ (primary endpoint), as well as blood levels of [^{13}C]-urea, ammonia and glutamine after AHA versus after non-AHA. When we evaluate the effect of AHA on each metabolite, the model will control for each metabolite's pretreatment level and will adjust variance estimates to account for the correlation between measurements on the same person as well as to take account of the random effect on the intercept. We will consider a relative AHA versus non-AHA difference in the time-averaged level of $^{13}\text{CO}_2$ of at least 20% as a signal that AHA can effectively reduce the impact of gut bacteria on urease activity. The presence of a clear effectiveness signal in healthy adults will be required before the crossover study can be implemented in adults with UCD.

Pilot data indicates that the expected level $^{13}\text{CO}_2$ in the absence of AHA treatment is 0.041% with a conservative precision of +/- 0.0075%. Therefore, using the sampsi procedure in Stata 12, a sample size of 8 crossover participants provides 90% power in 2-tailed testing at an alpha of 0.05 to detect a 20% relative (0.041% versus 0.033%)

difference in the time-averaged level of $^{13}\text{CO}_2$ on AHA versus non-AHA in either healthy or UCD affected adults.

7. Data Management

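### Order is randomised in Section 4 and fixed in Sections 1.1 and 2; if it is randomised, a stated 4:4 split and a study-day term would protect the AHA contrast cheaply.

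*Combined protocol and SAP*

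**What the plan says.** **Order.** Section 4 states: "A randomization table will determine if AHA or non-AHA will be performed first". The Appendix (10.1, AHA treatment information) says the dose is given in one of the two periods, "based on the randomization assignment determining whether treatment occurs in the first or the second treatment cycle". Neither gives an allocation ratio, a block size or the number per order.

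Other parts describe one order for everybody. Section 2 has two components, "the first without AHA, and the second after a single dose of AHA, 60mg/kg/d". Section 1.1 likewise assigns the baseline kinetics to the first occasion and AHA to the second. The primary outcome in the synopsis, a baseline measurement and then one after AHA, reads the same way.

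**Model.** Section 6 plans longitudinal linear regression of AHA versus non-AHA. It says "the model will control for each metabolite's pretreatment level and will adjust variance estimates" for same-person correlation, with a random intercept. No term for first versus second day, period or sequence is named.

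**Use of the result.** Section 6 treats a relative difference of at least 20% as the signal and requires a clear signal in the healthy adults before the UCD group is studied. On sample size it says "a sample size of 8 crossover participants provides 90% power in 2-tailed testing at an alpha of 0.05".

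**The concern.** In a two-period crossover each person's AHA-minus-non-AHA difference is also a difference between days. Two devices keep a day difference out of the result: equal numbers in the two orders, or a day term in the model. Section 4 does not state the first, and Section 6 does not name the second.

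With 8 people, the order split can easily be uneven by chance. Part of any day difference then sits inside the AHA estimate for that table. If the split happens to be even, the day difference cancels from the estimate but stays in the scatter of the 8 within-person differences and widens the standard error. The healthy-adult estimate is read against a 20% mark that bears on whether the second group is studied, so either effect could matter in a borderline case.

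The disagreement about order comes first. If everybody has AHA second, day and treatment are the same variable, and no model term can separate them.

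**Working it through.** **Inputs from Section 6.** Level without AHA 0.041%; target 20% relative, "to detect a 20% relative (0.041% versus 0.033%)", so 0.0082 at exactly 20% (0.008 as printed); n = 8 per group; two-sided alpha 0.05. The spread is described as "in the absence of AHA treatment is 0.041% with a conservative precision of +/- 0.0075%". The text does not say what this is. I take it as the SD of the within-person difference; it is also that SD if it describes a single level and the within-person correlation is 0.5.

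**1. The plan's own figure.** Paired normal approximation: n = [0.0075 × (1.960 + 1.282) / 0.0082]² = 8.79, so 9; with 0.008 it is 9.24, so 10. Power at n = 8 is 87.1% and 85.5%. The stated 8 is within two participants, but the 90% is not reached on this two-sided reading. With a t reference (7 df) power is 75.6% for 0.0082. That is a separate matter; 75.6% is the reference for what follows.

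**2. How a day difference enters.** Let δ be the fall from day 1 to day 2, n1 the number with AHA second and n2 the number with AHA first. With no day term, the mean within-person reduction is

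AHA effect + δ × (n1 − n2)/8.

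**3. How often the split is uneven.** Assuming simple 1:1 randomisation, Binomial(8, 0.5):

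| Split (either way) | Probability | Share of δ entering | Day shift needed to make 20% alone |
|---|---|---|---|
| 4:4 | 70/256 = 27.3% | 0 | none can |
| 5:3 | 112/256 = 43.8% | 0.25 | 80% |
| 6:2 | 56/256 = 21.9% | 0.50 | 40% |
| 7:1 | 16/256 = 6.3% | 0.75 | 27% |
| 8:0 | 2/256 = 0.8% | 1 | 20% |

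Uneven: 1 − 0.273 = 72.7%. 6:2 or worse: 74/256 = 28.9%. A fixed order behaves like the last row with certainty.

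**4. Effect on the 20% mark.** The documents give no day effect; I use 10% and 20% of the 0.041 level. SE = 0.0075/√8 = 0.00265. With a true AHA reduction of 10% (0.0041) and no leak, P(estimate ≥ 0.0082) = P(Z ≥ 0.0041/0.00265 = 1.55) = 6%. With a fall on day 2 and most people having AHA second:

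| Day fall | 4:4 | 5:3 | 6:2 | Fixed order |
|---|---|---|---|---|
| 10% | 6% | 12% | 22% | 50% |
| 20% | 6% | 22% | 50% | 94% |

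If most people have AHA first, the same shift lowers the estimate. For a 10% fall the probability drops from 6% to about 3% at 5:3 (z = 1.93) and 1% at 6:2 (z = 2.32).

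**5. Effect at 4:4.** For an assumed δ = 0.004 (about 10% of the level), the SD of differences rises to about √(0.0075² + 0.004²) = 0.0085. Simulation of the paired t-test, effect 0.0082:

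| δ | Power, no day term (7 df) | Power, day term (6 df) |
|---|---|---|
| 0 | 75.6% | 73.2% |
| 0.002 | about 73% | about 73% |
| 0.004 | about 65% | about 73% |

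At δ = 0.004 the type I error without the term is about 3%, so the test is conservative; with the term it is 5%.

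**6. Why both parts of the fix.** With a day term, the AHA estimate is the average of the two order-specific means, and the leak is zero for any split from 4:4 to 7:1. Its variance depends on the split, however: power is 73.2% at 4:4, 70.5% at 5:3 and 61.1% at 6:2. At 8:0 the term cannot be estimated.

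**7. Does the pretreatment covariate already do this?** Not reliably. Table 1 first samples ¹³CO₂ at time 0. If time 0 is the tracer dose, which the Appendix puts 60 minutes after AHA, that sample follows AHA on the AHA day. A level taken before the tracer also need not capture a day difference in the response to it.

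**The case against.** The strongest reply is that randomising order is itself the protection. If each person's order is randomised, the AHA estimate is unbiased over allocations, and a day shift widens the differences from which the standard error is computed. This stands. With δ = 0.004, no AHA effect, simple randomisation and no day term, the simulated type I error of the paired t-test is 5.0%. Even given an unfavourable 6:2 table it is 7%, and a null estimate reaches 20% about 1% of the time. The shift is as likely to work against AHA as for it.

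Second, the randomization table may be blocked. The documents do not say that it is not, and the study-design figure is not available in the text reviewed. This also stands: the supportable statement is that balance is not stated. Even a blocked table, though, leaves the precision loss in step 5.

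Third, the documents report no day effect, and carry-over of AHA looks small: 72 hours is at least 7.2 half-lives at 10 hours, leaving at most 0.7%. If there is no day effect, the extra term costs a little power for nothing. That is true, and it is why the point is a modest one.

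A reader might infer that the design biases the AHA effect, or that a day difference could open the UCD group by itself. The documents do not support either if order is randomised. The leak is conditional on an uneven table, and a day shift would have to be 80% of the level at 5:3, or 40% at 6:2, to produce the signal alone. Section 6 also asks for a clear signal, so the 20% mark need not be applied mechanically.

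**Conclusion.** The point holds as a low-cost improvement, with one contradiction to settle first. The sections disagree on whether order is randomised. Under the fixed order, the whole day effect is confounded with AHA, and a day term is not estimable.

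Under the randomised order, the plan states no 4:4 split and names no day term. The realistic consequences are lost precision (about 8 power points at 4:4 for a shift of 0.004) or a borderline estimate tipped across 20% in either direction when the table is uneven.

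The sizes rest on three assumptions: simple randomisation, 0.0075 as the SD of within-person differences, and day shifts of 10 to 20% chosen for illustration. The paired t-test stands in for the Section 6 model. The formula for the leak and the absence of a named day term depend on none of these.

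**What to change.** 1. Reconcile the synopsis, Sections 1.1 and 2 with Section 4 and the Appendix on whether order is randomised.
2. If it is, state in Section 4 that the table assigns 4 participants to each order within each group, as one permuted block of 8.
3. In Section 6, add study day (first or second) as a fixed effect beside AHA.
4. If the order is fixed, omit the day term and say in Section 6 that AHA and day cannot be separated.

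Cost: consistent wording on order, one sentence in Section 4 and one model term. The within-person contrast loses one degree of freedom (7 to 6). At 4:4 with no day effect, that is 75.6% − 73.2% = 2.4 power points. The two analyses have about equal power at a shift of 0.002, and the day term gains beyond that.
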